16.1.2.4.2 Determination of target lesion response

Table 16-1 Response criteria for target lesions

Response Criteria	Evaluation of target lesions
Complete Response (CR):	Disappearance of all non-nodal target lesions. In addition, any pathological lymph nodes assigned as target lesions must have a reduction in short axis to < 10 mm ¹
Partial Response (PR):	At least a 30% decrease in the sum of diameter of all target lesions, taking as reference the baseline sum of diameters.
Progressive Disease (PD):	At least a 20% increase in the sum of diameter of all measured target lesions, taking as reference the smallest sum of diameter of all target lesions recorded at or after baseline. In addition to the relative increase of 20%, the sum must also demonstrate an absolute increase of at least 5 mm ² .
Stable Disease (SD):	Neither sufficient shrinkage to qualify for PR or CR nor an increase in lesions which would qualify for PD.
Unknown (UNK)	Progression has not been documented and one or more target lesions have not been assessed or have been assessed using a different method than baseline. ³

SOD for CR may not be zero when nodal lesions are part of target lesions
 
Following an initial CR, a PD cannot be assigned if all non-nodal target lesions are still not present and all nodal lesions are <10 mm in size. In this case, the target lesion response is CR
 
In exceptional circumstances an UNK response due to change in method could be over-ruled by the investigator or central reviewer using expert judgment based on the available information (see Notes on target lesion response and methodology change in Section 16.1.2.2).
	

Notes on target lesion response

Reappearance of lesions: If the lesion appears at the same anatomical location where a target lesion had previously disappeared, it is advised that the time point of lesion disappearance (i.e., the “0 mm” recording) be re-evaluated to make sure that the lesion was not actually present and/or not visualized for technical reasons in this previous assessment. If it is not possible to change the 0 value, then the investigator/radiologist has to decide between the following possibilities:

- The lesion is a new lesion, in which case the overall tumor assessment will be considered as progressive disease
- The lesion is clearly a reappearance of a previously disappeared lesion, in which case the size of the lesion has to be entered in the CRF and the tumor assessment will remain based on the sum of tumor measurements as presented in [Table 16-1](#) above (i.e., a PD will be determined if there is at least 20% increase in the sum of diameters of **all** measured target lesions, taking as reference the smallest sum of diameters of all target lesions recorded at or after baseline with at least 5 mm increase in the absolute sum of the diameters). Proper documentation should be available to support this decision. This applies to patients who have not achieved target response of CR. For patients who have achieved CR, please refer to last bullet in this section.

- For those patients who have only one target lesion at baseline, the reappearance of the target lesion which disappeared previously, even if still small, is considered a PD.
- Missing measurements: In cases where measurements are missing for one or more target lesions it is sometimes still possible to assign PD based on the measurements of the remaining lesions. For example, if the sum of diameters for 5 target lesions at baseline is 100 mm at baseline and the sum of diameters for 3 of those lesions at a post-baseline visit is 140 mm (with data for 2 other lesions missing) then a PD should be assigned. However, in other cases where a PD cannot definitely be attributed, the target lesion response would be UNK.
- Nodal lesion decrease to normal size: When nodal disease is included in the sum of target lesions and the nodes decrease to “normal” size they should still have a measurement recorded on scans. This measurement should be reported even when the nodes are normal in order not to overstate progression should it be based on increase in the size of nodes.
- Lesions split: In some circumstances, disease that is measurable as a target lesion at baseline and appears to be one mass can split to become two or more smaller sub-lesions. When this occurs, the diameters (long axis - non-nodal lesion, short axis - nodal lesions) of the two split lesions should be added together and the sum recorded in the diameter field on the case report form under the original lesion number. This value will be included in the sum of diameters when deriving target lesion response. The individual split lesions will not be considered as new lesions, and will not automatically trigger a PD designation.
- Lesions coalesced: Conversely, it is also possible that two or more lesions which were distinctly separate at baseline become confluent at subsequent visits. When this occurs a plane between the original lesions may be maintained that would aid in obtaining diameter measurements of each individual lesion. If the lesions have truly coalesced such that they are no longer separable, the maximal diameters (long axis - non-nodal lesion, short axis - nodal lesions) of the “merged lesion” should be used when calculating the sum of diameters for target lesions. On the case report form, the diameter of the “merged lesion” should be recorded for the size of one of the original lesions while a size of “0”mm should be entered for the remaining lesion numbers which have coalesced.
- The **measurements for nodal lesions**, even if less than 10 mm in size, will contribute to the calculation of target lesion response in the usual way with slight modifications.
- Since lesions less than 10 mm are considered normal, a CR for target lesion response should be assigned when all nodal target lesions shrink to less than 10 mm and all non-nodal target lesions have disappeared.
- Once a CR target lesion response has been assigned a CR will continue to be appropriate (in the absence of missing data) until progression of target lesions.
- Following a CR, a PD can subsequently only be assigned for target lesion response if either a non-nodal target lesion “reappears” or if any single nodal lesion is at least 10 mm and there is at least 20% increase in sum of the diameters of all nodal target lesions relative to nadir with at least 5 mm increase in the absolute sum of the diameters.

- A change in method for the evaluation of one or more lesions will usually lead to an UNK target lesion response unless there is progression indicated by the remaining lesions which have been evaluated by the same method. In exceptional circumstances an investigator or central reviewer might over-rule this assignment to put a non-UNK response using expert judgment based on the available information. E.g. a change to a more sensitive method might indicate some tumor shrinkage of target lesions and definitely rule out progression in which case the investigator might assign an SD target lesion response; however, this should be done with caution and conservatively as the response categories have well defined criteria.

16.1.2.4.3 Determination of non-target lesion response

Table 16-2 Response criteria for non-target lesions

Response Criteria	Evaluation of non-target lesions
Complete Response (CR):	Disappearance of all non-target lesions. In addition, all lymph nodes assigned a non-target lesions must be non-pathological in size (< 10 mm short axis)
Progressive Disease (PD):	Unequivocal progression of existing non-target lesions. ¹
Non-CR/Non-PD:	Neither CR nor PD
Unknown (UNK):	Progression has not been documented and one or more non-target lesions have not been assessed or have been assessed using a different method than baseline ² .

1. The assignment of PD solely based on change in non-target lesions in light of target lesion response of CR, PR or SD should be exceptional. In such circumstances, the opinion of the investigator or central reviewer does prevail.
 
2. It is recommended that the investigator and/or central reviewer should use expert judgment to assign a Non-UNK response wherever possible (see notes section for more details)
	

Notes on non-target lesion response

- The investigator and/or central reviewer can use expert judgment to assign a non-UNK response wherever possible, even where lesions have not been fully assessed or a different method has been used. In many of these situations it may still be possible to identify equivocal progression (PD) or definitively rule this out (non-CR/Non-PD) based on the available information. In the specific case where a more sensitive method has been used indicating the absence of any non-target lesions, a CR response can also be assigned.
- The response for non-target lesions is **CR** only if all non-target non-nodal lesions which were evaluated at baseline are now all absent and with all non-target nodal lesions returned to normal size (i.e. < 10 mm). If any of the non-target lesions are still present, or there are any abnormal nodal lesions (i.e. ≥ 10 mm) the response can only be ‘**Non-CR/Non-PD**’ unless there is unequivocal progression of the non-target lesions (in which case response is **PD**) or it is not possible to determine whether there is unequivocal progression (in which case response is UNK).

Final

- Unequivocal progression: To achieve “unequivocal progression” on the basis of non-target disease there must be an overall level of substantial worsening in non-target disease such that, even in presence of CR, PR or SD in target disease, the overall tumor burden has increased sufficiently to merit discontinuation of therapy. A modest “increase” in the size of one or more non-target lesions is usually not sufficient to qualify for unequivocal progression status. The designation of overall progression solely on the basis of change in non-target disease in the face of CR, PR or SD of target disease is therefore expected to be rare. In order for a PD to be assigned on the basis of non-target lesions, the increase in the extent of the disease must be substantial even in cases where there is no measurable disease at baseline. If there is unequivocal progression of non-target lesion(s), then at least one of the non-target lesions must be assigned a status of “Worsened”. Where possible, similar rules to those described in [Section 16.1.2.4.2](#) for assigning PD following a CR for the non-target lesion response in the presence of non-target lesions nodal lesions should be applied.

16.1.2.4.4 New lesions

The appearance of a new lesion is always associated with Progressive Disease (PD) and has to be recorded as a new lesion in the New Lesion CRF page.

- If a new lesion is **equivocal**, for example because of its small size, continued therapy and follow-up evaluation will clarify if it represents truly new disease. If repeat scans confirm there is definitely a new lesion, then progression should be declared using the date of the first observation of the lesion
- If new disease is observed in a region which was **not scanned at baseline** or where the particular baseline scan is not available for some reason, then this should be considered as a PD. The one exception to this is when there are no baseline scans at all available for a patient in which case the response should be UNK, as for any of this patient's assessment (see [Section 16.1.2.5](#)).
- A **lymph node is considered as a “new lesion”** and, therefore, indicative of progressive disease if the short axis increases in size to ≥ 10 mm for the first time in the study plus 5 mm absolute increase.

FDG-PET: can complement CT scans in assessing progression (particularly possible for ‘new’ disease). See [Section 16.1.2.2](#).

16.1.2.5 Evaluation of overall lesion response

The evaluation of overall lesion response at each assessment is a composite of the target lesion response, non-target lesion response and presence of new lesions as shown below in [Table 16-3](#).

Table 16-3 Overall lesion response at each assessment

Target lesions	Non-target lesions	New Lesions	Overall lesion response
CR	CR	No	CR ¹
CR	Non-CR/Non-PD ³	No	PR
CR, PR, SD	UNK	No	UNK
PR	Non-PD and not UNK	No	PR ¹
SD	Non-PD and not UNK	No	SD ^{1, 2}
UNK	Non-PD or UNK	No	UNK ¹
PD	Any	Yes or No	PD
Any	PD	Yes or No	PD
Any	Any	Yes	PD

1. This overall lesion response also applies when there are no non-target lesions identified at baseline.
2. Once confirmed PR was achieved, all these assessments are considered PR.
3. As defined in [Section 16.1.2.4](#)

If there are no baseline scans available at all, then the overall lesion response at each assessment should be considered Unknown (UNK).

In some circumstances it may be difficult to distinguish residual disease from normal tissue. When the evaluation of complete response depends on this determination, it is recommended that the residual lesion be investigated (fine needle aspirate/biopsy) to confirm the CR.

16.1.3 Efficacy definitions

The following definitions primarily relate to patients who have measurable disease at baseline. [Section 16.1.3.2.8](#) outlines the special considerations that need to be given to patients with no measurable disease at baseline in order to apply the same concepts.

16.1.3.1 Best overall response

The best overall response is the best response recorded from the start of the treatment until disease progression/recurrence (taking as reference for PD the smallest measurements recorded since the treatment started). In general, the patient's best response assignment will depend on the achievement of both measurement and confirmation criteria.

The best overall response will usually be determined from response assessments undertaken while on treatment. However, if any assessments occur after treatment withdrawal the protocol should specifically describe if these will be included in the determination of best overall response and/or whether these additional assessments will be required for sensitivity or supportive analyses. As a default, any assessments taken more than 30 days after the last dose of study treatment will not be included in the best overall response derivation. If any alternative cancer therapy is taken while on study any subsequent assessments would ordinarily be

excluded from the best overall response determination. If response assessments taken after withdrawal from study treatment and/or alternative therapy are to be included in the main endpoint determination, then this should be described and justified in the protocol

Where a study requires confirmation of response (PR or CR), changes in tumor measurements must be confirmed by repeat assessments that should be performed not less than 4 weeks after the criteria for response are first met.

Longer intervals may also be appropriate. However, this must be clearly stated in the protocol. The main goal of confirmation of objective response is to avoid overestimating the response rate observed. In cases where confirmation of response is not feasible, it should be made clear when reporting the outcome of such studies that the responses are not confirmed.

- For non-randomized trials where response is the primary endpoint, confirmation is needed.
- For trials intended to support accelerated approval, confirmation is needed
- For all other trials, confirmation of response may be considered optional.
- The best overall response for each patient is determined from the sequence of overall (lesion) responses according to the following rules:
- CR = at least two determinations of CR at least 4 weeks apart before progression where confirmation required or one determination of CR prior to progression where confirmation not required
- PR = at least two determinations of PR or better at least 4 weeks apart before progression (and not qualifying for a CR) where confirmation required or one determination of PR prior to progression where confirmation not required
- SD = at least one SD assessment (or better) > 7 weeks after randomization/start of treatment (and not qualifying for CR or PR).
- PD = progression \leq 12 weeks after randomization/ start of treatment (and not qualifying for CR, PR or SD).
- UNK = all other cases (i.e. not qualifying for confirmed CR or PR and without SD after more than 6 weeks or early progression within the first 12 weeks)

The time durations specified in the SD/PD/UNK definitions above are defaults based on a 6 week tumor assessment frequency. However these may be modified for specific indications which are more or less aggressive. In addition, it is envisaged that the time duration may also take into account assessment windows. E.g. if the assessment occurs every 6 weeks with a time window of +/- 7 days, a BOR of SD would require a SD or better response longer than 5 weeks after randomization/start of treatment.

Overall lesion responses of CR must stay the same until progression sets in, with the exception of a UNK status. A patient who had a CR cannot subsequently have a lower status other than a PD, e.g. PR or SD, as this would imply a progression based on one or more lesions reappearing, in which case the status would become a PD.

Once an overall lesion response of PR is observed (which may have to be a confirmed PR depending on the study) this assignment must stay the same or improve over time until progression sets in, with the exception of an UNK status. However, in studies where confirmation of response is required, if a patient has a single PR (\geq 30% reduction of tumor burden compared to baseline) at one assessment, followed by a <30% reduction from baseline

at the next assessment (but not $\geq 20\%$ increase from previous smallest sum), the objective status at that assessment should be SD. Once a confirmed PR was seen, the overall lesion response should be considered PR (or UNK) until progression is documented or the lesions totally disappear in which case a CR assignment is applicable. In studies where confirmation of response is not required after a single PR the overall lesion response should still be considered PR (or UNK) until progression is documented or the lesion totally disappears in which case a CR assignment is applicable.

Example: In a case where confirmation of response is required the sum of lesion diameters is 200 mm at baseline and then 140 mm - 150 mm - 140 mm - 160 mm - 160 mm at the subsequent visits. Assuming that non-target lesions did not progress, the overall lesion response would be PR - SD - PR - PR - PR. The second assessment with 140 mm confirms the PR for this patient. All subsequent assessments are considered PR even if tumor measurements decrease only by 20% compared to baseline (200 mm to 160 mm) at the following assessments.

If the patient progressed but continues study treatment, further assessments are not considered for the determination of best overall response.

Note: these cases may be described as a separate finding in the CSR but not included in the overall response or disease control rates.

The best overall response for a patient is always calculated, based on the sequence of overall lesion responses. However, the overall lesion response at a given assessment may be provided from different sources

- Investigator overall lesion response
- Central Blinded Review overall lesion response
- Novartis calculated overall lesion response (based on measurements from either Investigator or Central Review)

The primary analysis of the best overall response will be based on the sequence of investigator/central blinded review/calculated (investigator)/calculated (central) overall lesion responses.

Based on the patients' best overall response during the study, the following rates are then calculated:

Overall response rate (ORR) is the proportion of patients with a best overall response of CR or PR. This is also referred to as 'Objective response rate' in some protocols or publications.

Disease control rate (DCR) is the proportion of patients with a best overall response of CR or PR or SD. The objective of this endpoint is to summarize patients with signs of "activity" defined as either shrinkage of tumor (regardless of duration) or slowing down of tumor growth.

Clinical benefit rate (CBR) is the proportion of patients with a best overall response of CR or PR, or an overall lesion response of SD or Non-CR/Non-PD which lasts for a minimum time duration (with a default of at least 24 weeks in breast cancer studies). This endpoint measures signs of activity taking into account duration of disease stabilization.

Another approach is to summarize the progression rate at a certain time point after baseline. In this case, the following definition is used:

Early progression rate (EPR) is the proportion of patients with progressive disease within 8 weeks of the start of treatment.

The protocol should define populations for which these will be calculated. The timepoint for EPR is study specific. EPR is used for the multinomial designs of (Dent and Zee 2001) and counts all patients who at the specified assessment (in this example the assessment would be at 8 weeks \pm window) do not have an overall lesion response of SD, PR or CR. Patients with an unknown (UNK) assessment at that time point and no PD before, will not be counted as early progressors in the analysis but may be included in the denominator of the EPR rate, depending on the analysis population used. Similarly when examining overall response and disease control, patients with a best overall response assessment of unknown (UNK) will not be regarded as “responders” but may be included in the denominator for ORR and DCR calculation depending on the analysis population (e.g. populations based on an ITT approach).

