Imaging assessments as described in [Table 8-3](#) should be performed at the time points specified using the same imaging modality used at baseline, irrespective of study treatment interruption or actual dosing (see [Table 8-2](#)). Imaging assessments for response evaluation will be performed every 9 weeks (+/- 7 days) through 45 weeks and every 12 weeks (+/- 7 days) thereafter until disease progression, death, lost to follow-up or withdrawal of consent. Imaging assessments should be scheduled using the randomization date as the reference date (not the date of the previous tumor assessment) and should be respected regardless of whether treatment with study treatment is temporarily withheld or unscheduled assessments performed.

Additional imaging assessments may be performed at any time during the study at the investigator's discretion to support the efficacy evaluations for a subject, as necessary. Clinical suspicion of disease progression at any time requires a physical examination and imaging assessments to be performed promptly rather than waiting for the next scheduled imaging assessment.

Each lesion that is measured at baseline must be measured by the same method (either same imaging method or by photography, including a metric ruler) and when possible, the same local radiologist/physician throughout the study so that the comparison is consistent. If an off-schedule imaging assessment is performed because progression is suspected, subsequent imaging assessments should be performed in accordance with the original imaging schedule.

Combined PET/CT may be used only if the CT is of similar diagnostic quality as a CT performed without PET, including the utilization of IV contrast media. At the discretion of the Investigators, FDG-PET scans may be performed to document progressive disease per RECIST 1.1 ([Section 16.1](#)).

The coded medical images will be used primarily for analysis as described in this protocol; however, the images may also be used for the development and evaluation of new analysis methods directly related to the area of research that this study covers.

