16.1.3.2.10 Sensitivity analyses

This section outlines the possible event and censoring dates for progression, as well as addresses the issues of missing tumor assessments during the study. For instance, if one or more assessment visits are missed prior to the progression event, to what date should the progression event be assigned? And should progression event be ignored if it occurred after a long period of a patient being lost to follow-up? It is important that the protocol and RAP specify the primary analysis in detail with respect to the definition of event and censoring dates and also include a description of one or more sensitivity analyses to be performed.

Based on definitions outlined in [Section 16.1.3.2.7](#), and using the draft FDA guideline on endpoints ([Clinical Trial Endpoints for the Approval of Cancer Drugs and Biologics, April 2005](#)) as a reference, the following analyses can be considered:

Table 16-5 Options for event dates used in PFS, TTP, duration of response

Situation		Options for end-date (progression or censoring) ¹ (1) = default unless specified differently in the protocol or RAP	Outcome
A	No baseline assessment	(1) Date of randomization/start of treatment ³	Censored
B	Progression at or before next scheduled assessment	(1) Date of progression (2) Date of next scheduled assessment ²	Progressed Progressed
C1	Progression or death after exactly one missing assessment	(1) Date of progression (or death) (2) Date of next scheduled assessment ²	Progressed Progressed
C2	Progression or death after two or more missing assessments	(1) Date of last adequate assessment ² (2) Date of next scheduled assessment ² (3) Date of progression (or death)	Censored Progressed Progressed
D	No progression	(1) Date of last adequate assessment	Censored
E	Treatment discontinuation due to 'Disease progression' without documented progression, i.e. clinical progression based on investigator claim	(1) Ignore clinical progression and follow situations above (2) Date of discontinuation (visit date at which clinical progression was determined)	As per above situations Progressed
F	New anticancer therapy given	(1) Ignore the new anticancer therapy and follow situations above (ITT approach) (2) Date of last adequate assessment prior to new anticancer therapy (3) Date of secondary anti-cancer therapy (4) Date of secondary anti-cancer therapy	As per above situations Censored Censored Event

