2.7.3 Handling of missing values/censoring/discontinuations

Regarding ORR:

- Subjects in the FAS with unknown BOR will be noted as such in the appropriate tables/listings and counted as non-responders in the ORR calculation.
- If there is no baseline tumor assessment, all post-baseline overall lesion responses are expected to be 'Unknown'. If no valid post-baseline tumor assessments are available, the BOR must be "Unknown" unless progression or death is reported.
- If any new anti-neoplastic therapy is taken while on study, any subsequent assessments would be excluded from the BOR derivation.

- Confirmed PR or CR reported prior to any additional anticancer therapy will be considered as responses in the calculation of the ORR irrespective of the number of missed assessments before response.

Regarding DOR:

- If progression or death due to any reasons has not occurred by the date of the cut-off, then the subject will be censored following the same rules defined for PFS in [Section 2.5.3](#).
- If a subject with a CR or PR has no progression or death, the subject is censored at the date of last adequate tumor assessment.

Regarding OS:

- The last date the subject was known to be alive is the last date the subject was contacted or seen by the treating team. If no post-baseline dates are available (before death or a censoring reason occurred), the date of randomization will be used.
- If a subject is not known to have died by the date of the cut-off, OS will be censored at the last date the subject was known to be alive.

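### The 12-week limit for a best overall response of PD comes from a 6-week scan schedule; on this trial's 9-week schedule some documented progressors are reported as Unknown

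*Protocol*

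**What the plan says.** Protocol 8.3.1 adopts the sponsor's response guideline (Protocol 16.1) for local tumor assessment and sets the schedule: "Imaging assessments for response evaluation will be performed every 9 weeks (+/- 7 days) through 45 weeks".

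Protocol 16.1.3.1 gives the BOR rules that concern time:

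- SD: "SD = at least one SD assessment (or better) > 7 weeks after randomization/start of treatment".
- PD: progression no later than "12 weeks after randomization/ start of treatment (and not qualifying for CR, PR or SD").
- UNK: all remaining cases, glossed as those "without SD after more than 6 weeks or early progression within the first 12 weeks" (and with no confirmed CR or PR).

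It then says that "The time durations specified in the SD/PD/UNK definitions above are defaults based on a 6 week tumor assessment frequency", and adds "However these may be modified for specific indications which are more or less aggressive". Its worked example takes the scan interval minus the window as the SD minimum.

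Protocol 12.5.1 and SAP 2.7.1 define BOR without any time limit for SD or PD, and SAP 4 declares no change from the protocol. For PFS, Protocol 12.4.1.3 and SAP 2.5.3 censor an event only if it follows two or more missing assessments. The default in Protocol Table 16-5 for "Progression or death after exactly one missing assessment" is an event at its actual date.

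**The concern.** The guideline ties its limits to scan frequency. Twelve weeks is the nominal second scan of a 6-week schedule, so there a subject who misses the first scan and progresses at the second is still PD. Here the second scan falls at weeks 17 to 19, beyond the limit, and the same subject drops into Unknown.

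The BOR table and the PFS event listing would then describe the same subject differently: Unknown in one, documented progression in the other. A reader of the BOR table would take Unknown to mean that no usable tumor information existed, when RECIST progression had been recorded.

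**Working it through.** **The guideline's own figures.** The window example is 6 × 7 − 7 = 35 days = 5 weeks, as stated. The PD limit is 2 × 6 = 12 weeks = 84 days, the nominal second scan.

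**Scan windows in this trial** (days elapsed from randomisation, Protocol 8.3.1):

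- First scan: 63 ± 7 = days 56 to 70 (weeks 8 to 10).
- Second scan: 126 ± 7 = days 119 to 133 (weeks 17 to 19).

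**Rules applied to a missed or UNK first scan followed by PD at the second:**

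| Schedule | PD at day | BOR, limit 12 weeks | BOR, limit 18 weeks | BOR, limit 19 weeks | PFS |
|---|---|---|---|---|---|
| 9-week | 119 | UNK | PD | PD | event |
| 9-week | 126 | UNK | PD | PD | event |
| 9-week | 133 | UNK | UNK | PD | event |
| 6-week | 84 | PD | – | – | event |

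An UNK scan is not an adequate assessment for PFS, but at most one assessment is missing, so the event stands. The 12-week default has no window allowance: on a 6-week schedule, PD at day 91 would also be UNK. On the 9-week schedule the whole second-scan window is lost.

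**Cases that are not affected:**

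- PD at the first scan (day 70 at the latest) is within 84 days: BOR = PD.
- SD at the first scan (day 56 at the earliest) exceeds 49 days: BOR = SD or better.
- Weeks 9 and 18 both missed, PD at week 27: BOR is UNK and PFS is censored, so the two agree.

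**The SD limits.** The SD line needs more than 7 weeks; the UNK line speaks of 6. No first scan at week 6 ± 7 days (days 35 to 49) can exceed 49 days, so the 7-week figure does not behave like a 6-week-schedule default. Carry-over from a 6-week schedule is therefore shown only for the PD limit. By the guideline's own example, this trial's SD minimum would be 9 × 7 − 7 = 56 days = 8 weeks.

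**Size.** Under the two-piece exponential model in Protocol 16.3 (75% progression-free at day 64):

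S(126) = 0.75 × exp(−λ₂ × 62), with λ₂ = ln(1.5) / (median in days − 64) and 30.4375 days per month (SAP 2.1.1.3).

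| Median PFS (months) | 1 − S(126) |
|---|---|
| 7.1 | 0.364 |
| 8.5 | 0.341 |
| 10.3 | 0.322 |
| 12.8 | 0.306 |

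The documents give no rate of missed or UNK week-9 scans. Multiplying 76 randomised subjects by 0.306 to 0.364 and by an assumed rate:

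- 5%: 1.2 to 1.4 subjects
- 10%: 2.3 to 2.8 subjects
- 15%: 3.5 to 4.2 subjects

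That is 0.306 × 5% = 1.5 to 0.364 × 15% = 5.5 percentage points of the FAS. These are upper figures, for reasons given under the verdict.

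**The case against.** The strongest reply is that no listed endpoint moves. PD and UNK both count as non-response and as non-control in the same FAS denominator, and the analysis is now descriptive. This stands, and it sets the limit on how serious the point is.

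A second reply is that BOR = PD denotes early progression, a different quantity from a PFS event, so the label is a convention. On the model above, between (0.306 − 0.25)/0.306 = 18% and (0.364 − 0.25)/0.364 = 31% of those with an event by week 18 were still event-free at day 64, and a 19-week limit would call such subjects PD. That is fair as far as it goes. But the guideline links its limits to scan frequency and, on its own schedule, accepts PD for a subject whose first usable scan is the second one. Keeping 12 weeks here departs from that logic without a stated reason.

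Third, the SAP's Introduction places derived-variable specifications in a separate programming document, which might hold adapted limits. It cannot be assumed to. Protocol 16.1.4.1 asks for study-specific decisions in the protocol or analysis-plan documentation, and the SAP contains none on this.

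Three stronger readings are tempting, and the documents do not support them:

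- **Bias between arms.** A reader might infer that the less tolerated arm misses more scans. No scan-completion figures by arm are given, and Protocol 8.3.1 schedules imaging regardless of treatment interruption.
- **A subject who fits no category.** The 6-week and 7-week figures disagree, but UNK takes all remaining cases, so a subject whose only SD scan falls between them is UNK.
- **A conflict with SAP 2.7.3.** Its exception, "unless progression or death is reported", applies only where no valid post-baseline assessment exists. The PD scan at the second visit is valid, so the clause neither rescues nor contradicts this case.

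**Conclusion.** The point holds as a minor, easily corrected fault. As written, a missed or UNK week-9 scan followed by RECIST PD at weeks 17 to 19 gives BOR Unknown, while PFS counts a progression. The PFS half assumes that neither subsequent anti-neoplastic therapy nor, in the combination arm, the sponsor's decision to discontinue capmatinib comes first.

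The effect is confined to the PD/Unknown split of the BOR analysis. ORR is unchanged. DCR is essentially unchanged: only an unscheduled SD scan at 7 to 8 weeks could move it, through the choice of SD minimum.

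The size is at most a few of 76 subjects, and it rests on the assumed 5% to 15% rate. It is an upper range because:

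- some modelled events are deaths;
- Protocol 8.3.1 calls for prompt imaging when progression is suspected, which may document PD before week 12;
- by default, scans more than 30 days after the last dose do not enter BOR;
- combination-arm scans after the sponsor's decision are excluded from the main BOR derivation;
- efficacy data are no longer captured after approval of amendment 03.

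The disagreement between the SD and UNK lines is a separate wording fault. Scheduled scans start at week 8, so it matters only for unscheduled scans.

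**What to change.** State the limits for this trial's schedule in SAP 2.7.1, in days elapsed from randomisation:

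- **SD:** at least one assessment of SD or better at 8 weeks or later (9 weeks − 7 days = 56 days), when CR or PR is not met. The wording must be at least 8 weeks, because a strict inequality would discard an in-window first scan on day 56.
- **PD:** progression within 19 weeks (2 × 9 weeks + 7 days = 133 days), when CR, PR or SD is not met. Eighteen weeks is not enough, because PD at day 133 is still in window.
- **UNK:** all other cases, citing the same two limits.

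The cost is a few lines of SAP text and a programming parameter, with no new data. One small downside: an unscheduled SD scan at 7 to 8 weeks, with no later SD, would no longer count towards DCR.
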